6.1.4 Handling of Treatment Errors and Discrepancies

In addition to the rules in [Section 6.1.3](#) for handling situations envisaged by the CTP, it is also possible that dosing errors may occur. These could either be errors in the site dispensing an incorrect treatment and/or giving incorrect instructions about how to take the dispensed treatment, or they could be patient administration errors.

Dosing errors will not change the assignment of any patient to actual maintenance treatment as described above, regardless of the reason for the error, and regardless of the unblinded dose taken or dispensed at the relevant week(s). However, any such errors and their unblinded doses will be identified as part of the analysis.

Blinded identification of potential discrepancies between assigned, dispensed and administered medication numbers will be performed prior to DBL as part of ongoing monitoring for possible IPDs. However, decisions on whether such discrepancies matter in practice (e.g. the BI 456906 dose taken was different from the intended BI 456906 dose, a patient randomised to placebo took an active BI 456906 dose, etc.), and whether the IPD is subsequently confirmed, require unblinding.

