7.2.5 Safety analyses

Adverse events will be coded using the Medical Dictionary for Drug Regulatory Activities (MedDRA). Standard BI summary tables and listings will be produced. All adverse events with an onset between start of treatment and end of the residual effect period (REP), a period of 28 days after the last dose of trial medication, will be assigned to the on-treatment period for evaluation.

Safety analyses will be performed on the Treated Set (TS), using the actual maintenance treatment received. Key safety analyses will also be performed using the randomised maintenance treatment (if this is different for any patient).

In general, safety analyses will be descriptive in nature and will be based on BI standards. No hypothesis testing is planned.

Statistical analysis and reporting of adverse events will concentrate on treatment-emergent adverse events, i.e. all adverse events occurring between start of treatment and end of the REP.

Frequency, severity, and causal relationship of adverse events will be tabulated by system organ class and preferred term after coding according to the current version of the Medical Dictionary for Drug Regulatory Activities (MedDRA) at database lock.

The adjudicated events specified in [Section 5.2.6.1.5](#) will be summarised descriptively for each treatment group.

Laboratory data will be analysed both quantitatively as well as qualitatively. The latter will be done via comparison of laboratory data to their reference ranges. Values outside the reference range as well as values defined as clinically relevant will be summarised. Treatment groups will be compared descriptively with regard to distribution parameters as well as with regard to frequency and percentage of patients with abnormal values or clinically relevant abnormal values.

Vital signs, physical examinations and 12-lead ECG observed at screening, baseline, during the course of the trial and at the end-of-trial evaluation will be assessed with regard to possible changes compared to findings before start of treatment.

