6.1.3 Actual Maintenance Treatment

According to the rules for escalating and adjusting the BI 456906 dose given in the CTP, it is envisaged that some patients may not receive the planned maintenance treatment according to the randomised treatment group, whilst nevertheless remaining on treatment.

Actual maintenance treatment will therefore be defined for analysis as follows:

- If the actual dose at the start of the maintenance period is known to be less than the planned maintenance dose to which the patient was randomised, then actual maintenance treatment will be defined as this dose at the start of the maintenance period (which is expected to be one of the lower planned maintenance doses).
- If the patient was known to have discontinued treatment during the dose escalation period, actual maintenance treatment will be defined as the next planned maintenance dose up from the last dose which was taken prior to the dose at the time of discontinuation. This is specified in the table below, for all dosing possibilities planned in the CTP. The same rule will be applied irrespective of the reason for discontinuing treatment during the dose escalation period.

Table 6.1.3: 1 Definition of actual maintenance treatment for patients randomised to active BI 456906 maintenance treatment who discontinued treatment during the dose escalation period

Dose at discontinuation / Previous dose	Actual maintenance treatment
0.3 mg / NA	0.6 mg
0.6 mg / 0.3 mg	0.6 mg
0.9 mg / 0.6 mg	2.4 mg
1.2 mg / 0.9 mg	2.4 mg
1.8 mg / 1.2 mg	2.4 mg
2.4 mg / 1.8 mg	2.4 mg
3.0 mg / 2.4 mg	3.6 mg
3.3 mg / 2.4 mg	3.6 mg
3.6 mg / 3.0 mg	3.6 mg
4.2 mg / 3.3 mg	3.6 mg
4.8 mg / 4.2 mg	4.8 mg

- In all other cases, actual maintenance treatment will be defined equal to planned maintenance treatment.
- All patients randomised to placebo maintenance treatment will be assigned to placebo for actual maintenance treatment.

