7.8 SAFETY ANALYSIS

All safety analyses will be performed on the TS, using actual maintenance treatment, and including only on-treatment data (unless otherwise specified in [Section 7.8.1](#)), regardless of whether early treatment discontinuation was COVID-19 related.

Selected AE summaries will also be presented on the TS using planned maintenance treatment. Where this is also planned, it is clearly specified.

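### SAP 6.1.3 and 6.1.4 disregard dosing errors when defining actual treatment, so a placebo patient mainly given active drug counts as placebo in every safety table, against protocol 7.2.5

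*SAP*

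**What the plan says.** Protocol 7.2.5 sets the grouping for safety: "Safety analyses will be performed on the Treated Set (TS), using the actual maintenance treatment received". It adds that key safety analyses are repeated by randomised treatment where the two differ.

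SAP 7.8 keeps the same label: "All safety analyses will be performed on the TS, using actual maintenance treatment, and including only on-treatment data". In the SAP, however, actual maintenance treatment is a derived variable, built as follows.

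- SAP 6.1.3 moves an active-arm patient known to start maintenance below the randomised dose: "then actual maintenance treatment will be defined as this dose at the start of the maintenance period". It classifies active-arm patients who stop during escalation by Table 6.1.3:1. Every other case defaults to the planned treatment.
- SAP 6.1.3 has one rule for the control arm: "All patients randomised to placebo maintenance treatment will be assigned to placebo for actual maintenance treatment".
- SAP 6.1.4 then deals with mistakes in dispensing or administering the drug: "Dosing errors will not change the assignment of any patient to actual maintenance treatment as described above, regardless of the reason for the error". This applies whatever the unblinded dose turns out to have been. Among its examples of a discrepancy is that "a patient randomised to placebo took an active BI 456906 dose".

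SAP 6.1.4 also says that errors and their unblinded doses will be identified in the analysis. SAP Section 7 (Disposition) has important protocol deviations (IPDs) summarised and listed by planned treatment. SAP Section 4 lists two changes from the protocol: no per-protocol analysis, and 1000 rather than at least 100 imputations. The dosing-error rule is not there.

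**The concern.** The protocol plans two views of safety, by treatment received and by randomised treatment, so that a difference between them can be seen. For a placebo patient mainly given active drug, the SAP sets both variables to placebo. The two views agree, and both put that patient's events under placebo. A table labelled as actual treatment then shows something other than treatment received, in a case that the SAP itself foresees.

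What is at stake is the placebo reference for adverse events, and most of all for rare serious or adjudicated events, where a single case in a column matters.

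**Working it through.** The documents state no dosing-error rate and no expected event rate, so there is no figure to reproduce. The check is a comparison of the rules, followed by arithmetic for scale.

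**Step 1. The rules applied to four patients**

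| Patient | Received (protocol 7.2.5) | SAP actual treatment | Conflict? |
|---|---|---|---|
| Active arm, starts maintenance on a lower dose under the titration rules | Lower dose | Lower dose (6.1.3) | No |
| Any arm, one wrong injection | Not clearly changed | Unchanged (6.1.4) | Not clear |
| Randomised to 0.6 mg, mainly given a higher dose in error | Higher dose | 0.6 mg (6.1.3, 6.1.4) | Yes |
| Placebo, mainly given active drug in error | Active | Placebo (6.1.3, 6.1.4) | Yes |

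The conflict is therefore limited to sustained errors. For the last patient, the planned-treatment tables also show placebo.

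**Step 2. Other outputs affected for that patient**

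- The pooled active column in safety tables (SAP 6.1.5) omits the patient.
- Exposure (SAP 7.7) uses the same variable.
- The QT-correction analysis (SAP 7.8.4) takes its off-drug values from patients randomised to placebo, so ECGs recorded on drug would be counted as off-drug.
- Protocol 4.1.5.1 gives the randomisation codes to bioanalytics so that placebo patients' PK and anti-drug-antibody samples can be left out. PK is therefore not planned to reveal the exposure, and kit reconciliation is the main safeguard.

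**Step 3. Opportunity for error**

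Dosing is weekly from day 1 to day 316 (flow chart footnotes): (316 − 1)/7 + 1 = 46 injection days. With two syringes each, that is 46 × 2 = 92 syringes for a completing patient. Protocol Appendix 10.1 uses five active strengths plus placebo, and five of its eleven dose levels pair an active with a placebo syringe. Protocol 7.2.1 names dispensing errors as a possible important deviation. None of this gives a rate.

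**Step 4. Scale**

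Input from the documents: 70 patients per arm (protocol 7.5), taken here as the treated number. Assumptions: k placebo patients mainly given active drug, event rate p on placebo, event rate q in those k patients.

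Placebo rate under the SAP rule = [(70 − k)p + kq]/70. Its shift from p is k(q − p)/70.

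| p | k | q | Placebo rate under SAP | Shift (points) |
|---|---|---|---|---|
| 5% | 1 | 50% | 5.64% | 0.64 |
| 5% | 1 | 100% | 6.36% | 1.36 |
| 5% | 5 | 100% | 11.79% | 6.79 |
| 20% | 1 | 50% | 20.43% | 0.43 |
| 20% | 1 | 100% | 21.14% | 1.14 |
| 20% | 5 | 100% | 25.71% | 5.71 |

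For example, with p = 5%, k = 5 and q = 100%: (65 × 0.05 + 5 × 1)/70 = 8.25/70 = 11.79%. If the k patients are grouped by treatment received, the placebo rate stays at p. One event that would not have occurred on placebo adds 1/70 = 1.43 points.

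**Step 5. Direction**

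For placebo patients given active drug with q > p, the placebo rate rises and the contrast with active shrinks. For a 0.6 mg patient given a higher dose, with more events at that dose, the 0.6 mg rate rises and its contrast with placebo grows.

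**The case against.** The strongest defence is that the protocol never defines the treatment received. It discusses the idea mainly for patients who tolerate only a lower maintenance dose, and SAP 6.1.3 handles exactly those. SAP Section 3 presents the SAP as a fuller elaboration of the protocol, so defining an open term need not count as a change for Section 4. Treatment is allocated through the interactive response system, kits are tracked by unique numbers, and compliance is checked at each clinic visit, so a long-running error would have to escape several checks. Errors and their doses will be reported. Safety is descriptive, with no hypothesis tests. A rule fixed in advance also avoids case-by-case decisions after unblinding.

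Much of this stands. A reader might infer that the SAP holds patients in their assigned column whatever they took. It does not: 6.1.3 moves active-arm patients for lower maintenance doses and for stopping during escalation. Nor does one stray injection clearly contradict the protocol. It would also be wrong to say that errors are recorded only as deviations.

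The sustained error remains. On any ordinary reading, a patient mainly given active drug did not receive placebo. Reporting the error makes it visible but leaves the tables unchanged. The benefit of a fixed rule is kept if a better rule is fixed in advance.

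**Conclusion.** The point holds for sustained dosing errors, and is clearest for placebo patients mainly given active drug. For them the SAP rule, followed as written, gives a safety column that disagrees with protocol 7.2.5, appears in both sets of tables, and is not declared in SAP Section 4.

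The total size is unknown because no error rate is given. Per patient it is at most 1/70, about 1.4 points, assuming 70 treated per arm and an event that would not have occurred on placebo. The larger shifts in the illustration need several such patients, and nothing in the documents suggests that number.

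A reader might infer a general bias toward no difference. The documents do not support that, since the direction depends on which arm was misdosed and how. This is a minor point, worth correcting because the case is foreseen and the correction is cheap.

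**What to change.** Amend SAP 6.1.4, for safety analyses only, and state the rule before unblinding:

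1. If unblinded kit records show that most injections were of a treatment other than the one assigned, place the patient in the column of the treatment mainly received. Count by injection day, adding the two syringes, because several active doses include a placebo syringe.
2. Place a placebo patient mainly given active drug in the planned maintenance dose group closest to the dose mainly taken, and in the pooled active column.
3. Move numerator, denominator and time at risk together, including in the exposure-adjusted adverse event table.
4. List adverse events of placebo patients with isolated active doses separately, without moving those patients.
5. Leave efficacy assignment unchanged and keep the planned-treatment adverse event tables.
6. Exempt such patients from the placebo rule in SAP 6.1.3 for safety, and apply the same classification to the off-drug values in SAP 7.8.4.

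If the sponsor prefers the present rule, the minimum is to declare it in SAP Section 4 and add a safety display by treatment received if such a case occurs.

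The cost is one rule applied to discrepancies that the sponsor already plans to confirm against unblinded doses. The downside is that a few patients may change column after unblinding, under a rule stated beforehand.

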6.1.5 Pooling Across Doses

In addition to displays by specific BI 456906 dose on descriptive summary tables, a pooled display across doses (i.e. “All BI 456906”) will also be presented.

Pooled BI 456906 dose will not be used in any statistical models or descriptive summaries of efficacy.

Pooled BI 456906 dose will be included on all disposition and demographic/baseline summary tables, and in descriptive summaries of treatment exposure and safety.

6.1.6 Definition of On-Treatment

It is particularly noted here that the protocol encourages continued study participation for patients who have discontinued treatment early. It is therefore expected that for some patients there will be off-treatment data captured during the planned treatment period.

In addition, even for patients who completed treatment according to the protocol, data captured during the follow-up period may be relevant for safety.

With these points in mind, it is important to be clear whether all available data will be used in a particular summary or analysis, or whether only on-treatment data will be used. The definition of “on-treatment” for this purpose is as described below. It is assumed that all patients will have

a date of last administration of study medication accurately recorded on the End of Treatment eCRF page.

“Off-treatment” refers to data which are captured after baseline but which are not “on-treatment” as defined below.

Safety

An AE start date or other safety assessment date will be considered “on-treatment” if the AE start date or assessment date is between the date of first dose and 28 days after the date of last dose of study treatment inclusive (the residual effect period (REP) is defined as 28 days in this trial).

The same on-treatment definition will be used for all types of safety data.

Efficacy

Efficacy data will also use the same 28 day definition of “on-treatment” as for safety.

The same on-treatment definition will be used for all types of efficacy data, including for all exploratory biomarkers (irrespective of whether the latter are specified as further endpoints or not).

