- Safety lab include haematology, clinical chemistry, infectious serology, lipids and urinalysis. For details refer to [Table 5.2.3:1](#). All blood samples should be collected before the administration of trial medication.
- PCR Test on SARS-CoV-2 to be performed at Visit 1
- FASTING sample: on these days, blood samples will also include some efficacy parameters including fasting glucose, insulin and C-peptide, and fasting lipid battery These visits would preferably be scheduled on mornings
- Centralized ECG. ECG should be recorded before blood samples are taken. ECG recording may be repeated by investigator for medical or quality reasons. ECG at follow up, only in case abnormal at previous visit. For ECG measurement, follow guidelines in [Section 5.2.4](#).
- PK and ADA/NAb sampling at trough prior to administration of next dose. In case of systemic hypersensitivity, also draw a plasma sample for IgE and ADA as detailed in the Lab Manual (ISF). Also include the evaluation of histamine, serum tryptase, and complement components
- Blood sample for exploratory biomarkers at Visit 2 should be collected before the administration of trial medication (pre-dose value)
- DNA biobanking requires one blood sample (preferably at Visit 2), serum and plasma samples are taken at several timepoints.
- PRO should be completed prior to assessment of vital signs and in the pre-specified order (ref to [section 6.2.2](#)) during respective visits
- Patient's material include paper food diary distributed at screening. Once patient is randomised distribute a scale to have home weight measurements and e-diary (on their own device or on a provided smartphone).
- 3 days food diary to be completed before the visit : includes two weekdays and one weekend day
- After the End Of Study visit (=individual patient's end of the study) the investigator should report only any cancers of new histology and exacerbations of existing cancer, trial treatment related SAEs and trial treatment related AESIs of which the investigator may become aware of and only via the BI SAE form.
- Visit 18 is organised only for the patient to collect his medication for the remaining 2 weeks. There is no need to visit the site staff other than pharmacy, and injection can be done at home. If, due to site organisation, the patient comes to the site and reports AEs, these will be recorded. Last drug injection will be on week 45, day 316.

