6.7 BASELINE, TIME WINDOWS AND CALCULATED VISITS

Definition of baseline

In general, baseline is defined as the last non-missing measurement on or prior to the first administration of study medication. In the case that the first dose of study medication is delayed beyond the date of randomisation, a post-randomisation value can be used as a baseline value provided that it meets the stated requirement.

Where clock times are available (expected to include laboratory safety data, 12-lead ECG, plasma BI 456906 concentrations and biomarkers) they will be used in addition to dates to define baseline, since it is also expected that the time of first study drug administration will be accurately recorded on the eCRF for all patients.

For vital signs, the baseline definition will make the additional requirement that the data records are pre-dose. In practice, this will also be done using the clock times as well as the date. Three pre-dose measurements are expected to be captured at the baseline visit (Visit 2); the mean of these 3 measurements (or the mean of the available measurements if fewer) will be used as baseline. In any situation in which only post-dose measurements are available at Visit 2 and no pre-dose measurements, Visit 2 will not be used as baseline; the mean of the 3 measurements (or those available if fewer) at the screening visit (Visit 1) will be used as baseline instead.

Unscheduled and repeat assessments (where available and relevant) are eligible for use as baseline values provided that they meet the above criterion.

Visit windows

All summaries and analysis which are presented by week will use a visit window to classify the data record, which is derived from the assessment date relative to a reference date, taken here to be the date of first administration of study medication. This approach allows appropriate classification of visits which may have occurred significantly earlier or later than the protocol assessment schedule, as well as the use of data captured at visits which have no fixed timing (notably the EOT visit). Relative day will be defined for this purpose as *(date of assessment – date of first administration of study medication) + 1*.

Nominal database visit labels will not be used in any summary or analysis by time point, unless otherwise stated.

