Prior to applying the visit windows specified below, it will first be determined whether the data record is on-treatment, as defined in [Section 6.1.6](#), for summaries or analysis which require this approach.

Unscheduled and repeat assessments (where relevant/available) are eligible for inclusion in visit windows.

For all variables except 12-lead ECG, if a patient has more than one non-missing value within the same visit window, the value closest to the target day will be selected. If two non-missing values are the same distance from the target day, the earlier of the two values will be selected.

For 12-lead ECG (only), scheduled visits take precedence over unscheduled visits. Once this rule has been applied, the measurement closest to the target day will be used. If there are two observations which have the same difference in days to the planned day (but are not on the same day), the later of the two values will be selected.

Derivation of last, minimum and maximum values where relevant in safety analyses will consider all available values, regardless of whether they were selected in the visit window.

The derivation of the maximum value of an ECG interval (or worst case of the morphological assessment, if applicable) will consider all on-treatment values (whether or not selected in any time window; see [Section 6.1.6](#) for definition of on-treatment).

Two different situations are envisaged, which are described in the following tables:

- Visit windows for variables scheduled to be assessed at all or many visits
- Visit windows for variables with a sparse visit schedule.

Table 6.7: 1 Visit windows for variables scheduled to be assessed at all or many visits

Period	Time Point	Target Day	Visit Window
Dose escalation	Week 2	15	2-21
	Week 4	29	22-35
	Week 6	43	36-49
	Week 8	57	50-63
	Week 10	71	64-77
	Week 12	85	78-91
	Week 14	99	92-105
	Week 16	113	106-119
	Week 18	127	120-133
Maintenance	Week 20	141	134-154
	Week 24	169	155-182
	Week 28	197	183-210
	Week 32	225	211-238
	Week 36	253	239-266
	Week 40	281	267-301
	Week 46	323	≥ 302

The relevant variables are expected to include body weight measured at the clinic and BMI derived from this, vital signs, routine non-fasting laboratory safety variables, 12-lead ECG and the mental health questionnaires (C-SSRS, PHQ-9).

These visits windows will also be used for waist circumference, although this is not scheduled to be captured at all weeks displayed.

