7.8.2 Laboratory data

The analyses of laboratory data will be descriptive in nature and will be based on BI standards. Central laboratory data will be used for all displays described below, unless otherwise specified. Summaries of eGFR and UACR will be included as part of the routine summaries of laboratory variables.

For continuous safety laboratory variables where reference ranges exist, normalised values will be derived (i.e. transformation to both a standard unit and to a standard reference range). Descriptive statistics will be presented over time for absolute values and changes from baseline in each of the laboratory variables where normalised values are possible. All scheduled weeks will be presented as well as last value, minimum value and maximum value on-treatment.

For continuous safety laboratory variables where reference ranges exist, a shift table will be produced summarising the shifts from baseline to the last value on treatment, and displaying categories “Low”, “Normal” and “High” with respect to the relevant reference range. Standardised values (i.e. transformation to a standard unit only) will be used for this purpose.

For categorical safety laboratory variables, a shift table will be produced summarising the shifts from baseline to the last value on treatment, and displaying each relevant category. For any semi-quantitative variables (i.e. those recorded as either “Normal” or with a continuous numerical value otherwise), the shift table will display categories “Normal” and “Abnormal” only, without further categorisation of the continuous values into different degrees of abnormality.

Potentially clinically significant abnormalities will be identified using BI standard rules. A listing containing these rules (including for each variable whether a low range applies, or a high range applies, or both) will be included in the CTR. A frequency table will be used to summarise the number and percentage of patients with potentially clinically significant abnormalities, for each variable where a BI standard rule exists. Patients with an abnormal value at baseline will be presented separately on this table.

A separate listing will present potentially clinically significant abnormal lab values; for each functional lab group all patient’s laboratory values will be listed, if there exists at least one value with clinically significant abnormality within the group.

The following additional investigations will be made for elevated liver enzymes:

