A frequency table will be produced of the following categories. A patient will be included in each relevant category, defined using the maximum post-baseline ALT and AST values observed on-treatment ([Section 6.1.6](#)), regardless of the baseline AST and ALT values:

- ALT or AST $\geq 3 \times$ ULN
- ALT or AST $\geq 5 \times$ ULN
- ALT or AST $\geq 8 \times$ ULN
- ALT or AST $\geq 10 \times$ ULN
- ALT or AST $\geq 20 \times$ ULN
- ALT or AST $\geq 3 \times$ ULN with total bilirubin $\geq 2 \times$ ULN.

In the above categories, each occurrence within a patient of a post-baseline elevation ALT or AST $\geq 3 \times$ ULN will be used as a trigger for the determination of the elevation of total elevation of bilirubin $\geq 2 \times$ ULN. The proposed time interval for the follow-up of total bilirubin is 30 days after the occurrence of the post-baseline ALT or AST elevation.

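### Read literally, SAP 6.1.6 makes the pre-dose Day 1 laboratory or ECG value on-treatment as well as baseline, which touches a few descriptive minimum and maximum displays

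*SAP*

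**What the plan says.** SAP 6.1.6 counts an AE start or safety assessment as on-treatment if its date is "between the date of first dose and 28 days after the date of last dose of study treatment inclusive", and adds: "The same on-treatment definition will be used for all types of safety data". No clock time or post-baseline condition is attached. Protocol 7.2.1 gives the same date rule.

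SAP 6.7 says that, in general, "baseline is defined as the last non-missing measurement on or prior to the first administration of study medication". Where clock times are available, as expected for laboratory and ECG data, "they will be used in addition to dates to define baseline"; the section does not use them for on-treatment status. The Protocol Flow Chart footnotes state: "All blood samples should be collected before the administration of trial medication". Protocol 5.2.4 likewise places the ECG before dosing.

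For extremes, SAP 6.7 states: "Derivation of last, minimum and maximum values where relevant in safety analyses will consider all available values", whether or not a visit window selected them. The ECG maximum draws on all on-treatment values. SAP 7.8.2 presents laboratory values and changes from baseline by week "as well as last value, minimum value and maximum value on-treatment". In the same section the liver-enzyme table is worded differently: "defined using the maximum post-baseline ALT and AST values observed on-treatment".

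**The concern.** The Day 1 pre-dose record satisfies both definitions. If it is kept in the on-treatment pool, each patient's on-treatment maximum is at least the baseline and the minimum at most the baseline. Change to maximum then cannot be negative, and change to minimum cannot be positive. A patient with no later sample would show as unchanged instead of missing. Because 7.8.2 writes post-baseline for ALT and AST but not for the other laboratory extremes, a programmer could reasonably conclude that the difference is deliberate.

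**Working it through.** **1. Tracing the record.** Relative day is assessment date minus first-dose date plus 1, so the first-dose day is Day 1. SAP 6.7 determines on-treatment status before applying windows. The first window in Table 6.7: 1 and in Table 6.7: 2 starts at Day 2, so Day 1 falls in none of them. Windowing therefore protects the by-week tables but not the last, minimum and maximum values.

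**2. Display by display, on the literal reading.**

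- Laboratory minimum and maximum (7.8.2): affected, with changes bounded at 0 as above.
- QTcF scatter plot of maximum change (7.8.4): floored at 0.
- QTcF shift table, baseline to maximum (7.8.4): no downward shift is possible. The effect is slight, because exclusion criterion 17 (Protocol 3.3.3) removes patients with QTc above 450 ms at screening or randomisation, so nearly all start in the lowest category.
- Last value and laboratory last-value shift table: affected only for patients with no later on-treatment sample.
- QTcF change categories (up to 30, over 30 to 60, over 60 ms): unaffected for a patient with a later ECG, since replacing a negative change by 0 stays in the lowest category. A simulation of 400,000 patients with an assumed SD of 10 ms moved none.
- By-week tables, liver-enzyme categories, ECG new-onset and notable-finding tables: unaffected.

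**3. Size for the maximum.** The documents give no figure to reproduce, so this is an illustration. Let *b* be the baseline and *M* the largest of *k* later values, all independent normal with unit within-patient SD, the later ones shifted by δ. Without baseline in the pool the change is *M* − *b*; with it, max(*M* − *b*, 0). The inflation is the mean of max(*b* − *M*, 0). *k* = 16 is the number of windows in Table 6.7: 1; the other *k* and δ are assumptions. Results from 400,000 simulated patients per row, in SD units, with inflation computed before rounding:

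| k | δ | baseline is the maximum | mean change, baseline excluded | included | inflation |
|---|---|---|---|---|---|
| 16 | 0 | 5.9% | 1.767 | 1.795 | 0.028 |
| 16 | −1 | 25.2% | 0.765 | 0.933 | 0.168 |
| 16 | +1 | 0.7% | 2.769 | 2.772 | 0.002 |
| 4 | 0 | 20.0% | 1.029 | 1.162 | 0.133 |
| 4 | −1 | 49.4% | 0.028 | 0.501 | 0.473 |
| 4 | +1 | 4.7% | 2.027 | 2.050 | 0.023 |
| 1 | 0 | 50.1% | −0.001 | 0.563 | 0.565 |
| 1 | −1 | 75.9% | −0.996 | 0.200 | 1.196 |
| 1 | +1 | 24.0% | 0.999 | 1.199 | 0.200 |

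Checks: with δ = 0 the probability should be 1/(*k* + 1), which is 1/17 = 5.9%, 1/5 = 20% and 1/2 = 50%. For *k* = 1 and δ = 0 the inflation should be 1/√π = 0.564. Both agree. The minimum gives the mirror image with the sign of δ reversed.

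**4. Difference between an unshifted and a shifted group, k = 16.** For a 1 SD fall: 1.767 − 0.765 = 1.002 without baseline and 1.795 − 0.933 = 0.862 with it, a shrinkage of 0.140/1.002 = 14%. For a 1 SD rise: 2.769 − 1.767 = 1.002 against 2.772 − 1.795 = 0.977, about 2.5%.

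**5. Last value.** If *n*₀ of *n* patients have no later sample and are counted as zero change, the mean is multiplied by (*n* − *n*₀)/*n*. For *n* = 350 this is 349/350 = 0.997 with one such patient and 340/350 = 0.971 with ten. For one patient in an arm of 70 it is 69/70 = 0.986.

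**The case against.** The strongest reply is that the SAP already treats baseline and on-treatment as separate classes. SAP 6.1.6 confines off-treatment to data captured after baseline, which frames the on/off split as a post-baseline one. SAP 7.8.4, on the QT correction model, names baseline and on-treatment values as alternatives while citing 6.1.6. The ALT/AST wording can be read as showing the general convention. A reader might infer from 6.1.6 alone that the sponsor intends to count baseline as on-treatment; these passages do not support that. They are not an operative exclusion, however: the first defines only off-treatment, and the others concern single analyses. The gap stands; the intention does not.

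A reader might also infer that last values are generally distorted. They are not, because any later on-treatment sample replaces Day 1. Laboratory tests are scheduled throughout treatment, and patients who stop early are due an end-of-treatment visit about 7 days after the last dose.

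Finally, the larger figures concern the maximum of a falling variable or the minimum of a rising one. The extreme in the direction of the shift hardly moves. This objection stands in full, and it rules out presenting 14% as a general loss in the safety comparisons.

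**Conclusion.** The point holds as a minor wording gap. The rule in 6.1.6, followed to the letter, admits the Day 1 pre-dose record to the on-treatment pool, and nothing in 6.7, or in the laboratory minimum/maximum and ECG maximum text of 7.8.2 and 7.8.4, takes it out. With 16 later samples the inflation of the mean change to maximum is about 0.03 SD without a shift, 0.17 SD for a 1 SD fall and 0.002 SD for a 1 SD rise. With four samples the corresponding figures are 0.13, 0.47 and 0.02 SD. All rest on assumed independence, normality and shift sizes. The documents supply no drug effect on these variables and no sampling pattern by arm, so they do not show that arms would in fact be distorted differently. The affected displays are descriptive, and no hypothesis test depends on them.

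**What to change.** In SAP 6.1.6, keep the date rule for AE start dates. For all other safety assessments, require on-treatment values to be after the first administration, using the clock times that 6.7 already uses to identify baseline. Write post-baseline into the last, minimum and maximum derivations in 6.7, 7.8.2 and 7.8.4, as 7.8.2 already does for ALT and AST. State that patients with no post-baseline value are shown as missing in the change and shift displays.

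The cost is a short clarification and one condition in the derivation program. No new data are needed, since 6.7 expects clock times for laboratory, ECG and first-dose records. There is no analytical drawback.
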